11.3.9 Subjects with any Rescue Therapy Use

Population: Full Analysis Set, Per Protocol Set (for Core Phase only)

Target Phases: Core Phase, Extension Phase

Analysis items: - Rescue therapy (Yes/No)

Contents: - The number of subjects with rescue therapy (Yes/ No) and its proportion with 95% CI are calculated.

Definitions: - Rescue therapy (Yes): The number of subjects who use at least one rescue therapy after the first administration of study drug in each phase (Core Phase (26-week treatment period) or Extension Phase).

- If one subject takes the same therapy in both Core Phase and Extension Phase (e.g. the end date of rescue therapy in Core Phase is ongoing), that subject will be counted in Core Phase and Extension Phase respectively.
- The denominator to calculate the proportion is the target population (the number of subjects in Full Analysis Set/Per Protocol Set)
- Rescue therapy will be defined as the addition of any new ITP medication or medication to treat thrombocytopenia (examples below). TPO receptor agonists are not allowed as rescue therapy.

- Corticosteroids (ATC level 2 = “CORTICOSTEROIDS FOR SYSTEMIC USE”)
- Intravenous immunoglobulin (IVIg) therapy (ATC level 2= “IMMUNE SERA AND IMMUNOGLOBULINS”)
- Anti-D therapy (PT = “Anti-D (rh) immunoglobulin”)
- Mycophenolate mofetil (PT = “Mycophenolate mofetil”)
- Azathioprine (PT = “Azathioprine”)
- Danazol (PT = “Danazol”)
- Cyclosporin A (PT = “Ciclosporin”)
- Platelet transfusion (concomitant procedure as “TRANSFUSIONS”)
- Any increase in baseline dose of a concomitant ITP medication
- Regarding 95% CI for binomial proportions, refer to [8.3.2 Proportion and Confidence Intervals for proportions.](#)

11.3.10 Subjects with a Reduction/Discontinuation in use of Concomitant ITP Medications from Baseline

Population: Full Analysis Set, Per Protocol Set

Target Phases: Core Phase

Analysis items: - Reduction in use of concomitant ITP medications

- Discontinuation in use of concomitant ITP medications

Contents: - Calculate the number of subjects who have a reduction/discontinuation of Concomitant ITP medications after baseline.

For each item, the denominator is as below

| Items | The denominator of percentage |
|--|---|
| 
 • Reduction of Concomitant ITP medications after baseline • Discontinuation of Concomitant ITP medications after baseline | The number of subjects who used concomitant ITP medications at baseline |

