Definitions: ITP medications are defined as the medications with ATC level 2 = “CORTICOSTEROIDS FOR SYSTEMIC USE”

Baseline ITP medications are defined as the ITP medications that are taken on the day of first administration; and concomitant ITP medications use at Core Phase are defined as ITP medications that start after the day of first administration and up to the last day of 26-week treatment period (excluding dose-tapering period) of Core Phase.

Only subjects with use of concomitant ITP medications at baseline will be included in the analysis. If a subject has use of concomitant ITP medication at baseline and has all post-baseline total daily doses for same medications (by PT) reduced without later increasing to the baseline or higher dose, or has no use of concomitant ITP medication post-baseline during 26-week

treatment, this subject is considered as having a reduction in use of concomitant ITP medication from baseline.

Subjects who discontinue all concomitant ITP medications before the last dose date of 26-week treatment will be considered as having a discontinuation of concomitant ITP medications.

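### SAP 11.3.10 counts only systemic corticosteroids as ITP medication, so its reduction/discontinuation endpoint omits four drugs the protocol permits; its reduction rule is also unclear

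*SAP*

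**What the plan says.** SAP 11.3.10 summarises subjects whose concomitant ITP medication is reduced or discontinued during the Core Phase. Its parts are:

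- **Scope.** "ITP medications are defined as the medications with ATC level 2" for systemic corticosteroids. SAP 10.1 footnote a uses the same class for the baseline characteristic.
- **Baseline.** "Baseline ITP medications are defined as the ITP medications that are taken on the day of first administration".
- **Post-baseline use.** "concomitant ITP medications use at Core Phase are defined as ITP medications that start after the day of first administration", up to the end of the 26-week period.
- **Reduction.** There are two routes. By the first, a baseline user qualifies who "has all post-baseline total daily doses for same medications (by PT) reduced without later increasing to the baseline or higher dose". The second route is to have taken no such drug at all after baseline.
- **Discontinuation.** "Subjects who discontinue all concomitant ITP medications before the last dose date of 26-week treatment" qualify.
- **Denominator.** "The number of subjects who used concomitant ITP medications at baseline".

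The endpoint as listed in Protocol 3.3 (discontinuation) and SAP 3.3.3 (reduction or discontinuation) refers to concomitant ITP medications without naming a class. SAP 5.1 declares the added reduction endpoint and the change to bleeding events of special interest. It does not mention a restriction to steroids.

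**The concern.** Lowering the need for concomitant ITP medication is a stated goal of dose modification (Protocol 4.1), and the Core Phase has a 12-week period for it. The endpoint should therefore cover the drugs that the protocol lets subjects bring in and taper. A steroid-only definition covers one of five, and nothing in the plan says why. It affects discontinuation, which is the protocol's own endpoint, as well as the reduction measure that the SAP adds.

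The second worry is the scoring rule. Two careful programmers could follow SAP 11.3.10 and obtain different reduction counts from the same data, because the text does not settle whether a drug continuing from before Day 1 counts as post-baseline use, or whether doses taken before a taper count against it.

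**Working it through.** The plan gives no figure for this endpoint, so there is nothing to reproduce. The check sets the provisions side by side and applies the rule to simple dose histories.

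**Scope**

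- Permitted background (Protocol 6.5.2; exclusion criteria 11 and 12 admit stable users): corticosteroids, azathioprine, mycophenolate mofetil, cyclosporin A, danazol, which makes 5.
- Counted in SAP 10.1 footnote a and SAP 11.3.10: systemic corticosteroids, which makes 1.
- Omitted: 5 − 1 = 4. SAP 11.3.9 already codes all four by preferred term for rescue therapy (for example, the entry beginning "Azathioprine (PT").

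Following the text exactly:

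1. Azathioprine alone at baseline, whether stopped or unchanged: not in the denominator.
2. Steroid plus azathioprine, steroid stopped, azathioprine unchanged: scored as having discontinued all ITP medication.
3. Systemic steroid given for another indication: counted as ITP therapy, because the definition uses the drug class and not the indication.

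The subgroups in SAP 11.1.2, 13.2.2 and 13.2.5 split subjects by use of concomitant ITP medications. They neither say at baseline nor cite footnote a. If they use the footnote a flag, subjects like case 1 fall under No.

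**Reduction rule**

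Protocol 4.3.2 bars tapering of ITP medication in the Titration Period except for a safety concern. Protocol 6.5.3 places tapering in Visits 8 to 13. In SAP 8.6 the target days are Day 42 for Visit 8 and Day 112 for Visit 13. A subject who tapers on Day 42 has taken the baseline dose on Days 2 to 41, that is 41 − 2 + 1 = 40 post-baseline days. One who tapers on Day 112 has 111 − 2 + 1 = 110 such days.

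| Steroid history | Only records beginning after Day 1 count | Every dose from Day 2 counts | Sequence: dose falls below baseline and does not return |
|---|---|---|---|
| Unchanged, one record from before Day 1 | reduced (wrong) | not reduced | not reduced |
| Lowered on Day 56, new record at the lower dose | reduced | not reduced (wrong) | reduced |
| Stopped on Day 111 | reduced | not reduced (wrong) | reduced |

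Under the middle reading the third subject is discontinued but not reduced. The first reading also depends on data entry: if the unchanged drug is re-entered after Day 1 at the same dose, it is scored correctly as not reduced. These histories show the logic only; they say nothing about how often each case occurs.

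SAP 10.3 counts as concomitant any drug begun before first dose and still continuing, so the first reading also conflicts with the SAP's general definition.

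**Weight of one subject**

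Baseline use is not given, so the denominator n is an assumption. With n fixed, one subject scored wrongly moves the rate by 100/n points: 100/5 = 20.0, 100/10 = 10.0, 100/19 = 5.3. The last would mean that all 19 planned subjects took a counted drug at baseline.

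**The case against.** The reduction rule can be defended. The discontinuation rule only makes sense if drugs continuing from baseline count as concomitant, SAP 10.3 says so in general, and the bar on a later increase implies that doses are read in order. On that sequence reading none of the histories above is misclassified. Much of this stands, and it is why the reduction rule is the lesser fault. What remains is that the sequence reading departs from the words of SAP 11.3.10 and is nowhere stated.

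A reader might infer that the reported reduction rate will be inflated, or that both scoring errors will appear together. The documents do not support this. The two errors come from different readings, and the first also needs a record structure that the documents do not describe.

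A reader might also take the low-dose steroid clause in Protocol 6.5.3 to describe a subject who stops azathioprine on a steroid that was never lowered, and who is then scored as not reduced. The clause is an exception to finishing one drug before tapering a second. Its natural case is a steroid already lowered, which the sequence reading scores as reduced.

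On scope, the defence is that the restriction is printed openly in two places, that Listing 16.2.4.5 shows all prior and concomitant medication and so allows a hand check, and that perhaps only steroids were used. The first two are true, but they do not align the analysis with the endpoint as worded. The documents do not say the third.

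**Conclusion.** Wrong as written, and worth fixing. The scope defect follows from the text alone: four permitted drugs are left out, the endpoint wording carries no such limit, and SAP 5.1 does not list it. The reduction rule is a secondary drafting defect that one clear statement would cure.

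The effect on the reported rates cannot be computed. The scope error is nil if no subject takes any of the four other drugs and no systemic steroid is given for another indication. Any effect on the subgroups is conditional on their using the footnote a flag.

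A reader might infer that the main result is at risk. It is not. This is a descriptive endpoint without testing (SAP 8.3.5), rescue therapy has its own drug list in SAP 11.3.9, and nothing carries the steroid-only definition back into that list. The primary endpoint, the 8.02-week hurdle and the sample size are unaffected.

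**What to change.** 1. In SAP 10.1 and 11.3.10, define ITP medication as the Protocol 6.5.2 drugs given for ITP, using the SAP 11.3.9 codes and the recorded indication. Apply the same baseline flag to the subgroups, and record the definition in SAP 5.1.
2. Count as post-baseline use any such record active after Day 1, including records begun earlier.
3. Score a reduction when a drug's total daily dose falls below its baseline, or the drug stops, and does not return to baseline or higher by the end of the 26-week period. Do not treat a switch to another systemic corticosteroid as a stop, and say how doses are compared across a switch.
4. Score discontinuation only when all baseline ITP drugs have stopped and no ITP drug, including a newly started one, is in use at the end of the 26-week period.
5. State whether one reduced drug is enough for a subject on two or more, and how a subject who leaves before Week 26 is scored.

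The cost is SAP wording and slightly more derivation work. Dose, indication and dates are already collected (Protocol 6.5.6). The reported rate may turn out lower. Declaring and justifying a steroid-only scope in SAP 5.1 would be simpler, but the result would then have to be labelled as steroid reduction and would not be the endpoint listed in Protocol 3.3.

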### 4 STUDY DESCRIPTION

# 4.1 Summary of Study Design

This study is an open-label study of avatrombopag in Japanese men and women  $\ge 18$  years who have chronic ITP. Approximately 19 subjects who meet all the eligibility requirements will be enrolled. The Screening Visit and Day 1 Baseline Visit platelet counts will be averaged to obtain the baseline platelet count value. The 2 samples must be obtained  $\ge 48$  hours and  $\le 2$  weeks apart and the results must be available prior to enrollment. No single platelet count can be  $> 35 \times 10^9 / L$ . An additional screening platelet count is required if the second platelet count is outside of the 2-week window.

Subjects will receive a starting dose of 20 mg avatrombopag once daily and will be allowed to change their dose and dosing frequency (maximum dose 40 mg daily, minimum dose 20 mg once weekly) in accordance with their individual platelet responses. The overall goal of any dose modification will be to maintain the platelet count  $\geq 50 \times 10^9/L$  and  $< 200 \times 10^9/L$ , and to decrease the need for concomitant ITP medications.

The study will consist of 3 phases: Pre-enrollment, Primary Investigation (Core Phase), and Extension. The Pre-enrollment Phase will have 1 Screening Period (up to 4 weeks). The Primary Investigation Phase (Core Phase) will have 4 periods: Baseline (1 day), Titration (6 weeks), Concomitant ITP Medication Reduction (12 weeks), and Maintenance (8 weeks including the Endof-Treatment [EOT] Visit). Subjects will have weekly or bi-weekly visits during the 26-week Primary Investigation Phase (Core Phase) to collect the required platelet count data, bleeding events, and other AEs. All subjects who complete the Primary Investigation Phase (Core Phase) can continue to receive avatrombopag in the Extension Phase until market authorization in Japan. Safety and efficacy data will be collected monthly in the Extension Phase. Dose-tapering and Follow-up at the end of the Core Phase are required only for those subjects not continuing into the Extension Phase.

The total study duration of the Pre-enrollment and Primary Investigation Phase will be up to 7 months. Subjects may continue in the Extension Phase until market authorization in Japan.

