11.3 Other Efficacy Endpoints

11.3.1 Durable Platelet Response

Population: Full Analysis Set, Per Protocol Set

Target Phases: Core Phase

Analysis items: - Durable platelet response

Contents: - The number of responders/non-responders and its proportion with 95% CI is calculated.

Definitions: - Responders (Yes): Subjects who have at least 6 of 8 (i.e., $\geq 75\%$) weekly platelet counts $\geq 50 \times 10^9 / L$ during the last 8 weeks (from Visit 15 (Week 19) to Visit 22 (Week 26)) of treatment over the 26-week treatment period and not taking any rescue therapy.
- Non-responders (No): Subjects who have less than 6 weekly platelet counts $\geq 50 \times 10^9 / L$ during the last 8 weeks over the 26-week treatment

- period or taking any rescue therapy.
- Regarding the data handling:
 - 1. Subjects who have missing platelet assessments at scheduled visits of interest will be considered as non-responder at any given time point.
 - 2. Subjects who use rescue therapy at any time during 26-week treatment period will be considered as non-responders for all subsequent days after rescue therapy start date.
 - 3. Subjects who discontinue the study or who are lost to follow-up before 26 weeks will have all subsequent unobserved scheduled platelet assessments at the scheduled time points as having “missing” platelet values.
- Regarding 95% CI for binomial proportions, refer to [8.3.2 Proportion and Confidence Intervals for proportions](#).
- Regarding Rescue therapy, refer to table [11.3.9 Subjects with any Rescue Therapy Use](#)

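### SAP 11.3.10 counts a discontinuation of concomitant ITP medication without requiring that the steroid stays stopped, and without regard to later rescue

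*SAP*

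**What the plan says.** SAP 11.3.10 defines two outcomes among subjects on ITP medication at baseline.

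- **Discontinuation:** "Subjects who discontinue all concomitant ITP medications before the last dose date of 26-week treatment will be considered as having a discontinuation". No further condition follows.
- **Reduction:** a subject qualifies if all post-baseline daily doses of the same drug, by preferred term, are "reduced without later increasing to the baseline or higher dose", or if there is no post-baseline use at all.

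The terms behind both outcomes come from the same section:

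- **Drug class:** "ITP medications are defined as the medications with ATC level 2" equal to systemic corticosteroids. IVIg, anti-D, platelet transfusion, azathioprine, mycophenolate, danazol and ciclosporin are outside it.
- **Steroids begun on study:** "concomitant ITP medications use at Core Phase are defined as ITP medications that start after the day of first administration", up to the end of the 26-week period.
- **Denominator:** "The number of subjects who used concomitant ITP medications at baseline".

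Rescue is a separate endpoint in SAP 11.3.9: "Rescue therapy will be defined as the addition of any new ITP medication or medication to treat thrombocytopenia". Its list includes corticosteroids, IVIg and platelet transfusion. SAP 11.3.10 does not refer to it. By contrast, the durable-response definition in SAP 11.3.1 requires qualifying counts during "treatment over the 26-week treatment period and not taking any rescue therapy". The protocol's own wording of the discontinuation endpoint (Sections 3.3 and Synopsis) has neither a restart condition nor a rescue condition.

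**The concern.** Protocol 4.1 makes it part of the aim of dose modification "to decrease the need for concomitant ITP medications". A reader of the discontinuation proportion will take it as the share of steroid users who could do without the steroid. A withdrawal that fails, with a relapse and renewed treatment, is what the proportion should separate from success. As written, it can be counted as success.

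The two outcomes in the section also do not fit together. Reduction has a clause against going back up; discontinuation has none. Discontinuation is the stronger outcome, yet a subject can meet it and fail the weaker one.

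**Working it through.** The plan gives no rate, sample size or test for this endpoint, so there is no figure to reproduce. The check applies the rule as worded to example subjects.

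**Inputs.** The last dose is taken as Day 182, the Visit 22 target in SAP 8.6. The baseline steroid is stopped on Day 80, which lies between Week 6 and Week 16, when Protocol 6.5.3 allows down-titration. Later events start on Day 100. These days are chosen for illustration.

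**Two readings.** Under reading (a), the word 'all' covers both the baseline steroid and any steroid started on study. This is the plain reading, because steroids started after the first dose fall within the defined term. Under reading (b), only the baseline steroid is checked.

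| After stopping on Day 80 | Discontinued, (a) | Discontinued, (b) | Discontinued if the steroid must stay stopped |
|---|---|---|---|
| No relapse | Yes | Yes | Yes |
| IVIg on Day 100 | Yes | Yes | Yes, shown as later rescue |
| Platelet transfusion on Day 100 | Yes | Yes | Yes, shown as later rescue |
| New steroid course, Days 100 to 128 | Yes | Yes | No |
| New steroid from Day 100, ongoing on Day 182 | No | Yes | No |

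**IVIg and transfusion.** They cannot change the result on either reading, because they are not ITP medications for this section.

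**Repeat steroid course.** A course on Days 100 to 128 ends before Day 182, so every steroid record has stopped and the subject is discontinued: Yes. If it is the same steroid by preferred term, at or above the baseline dose, the reduction rule is broken and the subject is reduced: No. One such subject adds 1 to the discontinuation count and 0 to the reduction count.

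**Direction.** A stay-off condition can only remove subjects from the discontinued group. Measured against such a definition, the present rule can only overstate the proportion.

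**Size.** One subject moves the proportion by 100/n percentage points, where n is the number of baseline users. The documents do not give n. Assume 4 to 19, the top being the planned enrolment:

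- n = 4: 100/4 = 25.0 points
- n = 10: 100/10 = 10.0 points
- n = 19: 100/19 = 5.3 points

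These are effects per subject. The documents do not allow an estimate of how many subjects would be affected.

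**The case against.** A fair defence has several parts, and much of it stands.

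- **Ongoing steroid.** A reader might infer that any new steroid course after the stop still counts as success. On the plain reading of 'all', a course still running at the last dose date fails. Only a completed course gets through, and that subject is off steroids at the end.
- **Last-minute stop.** The wording alone would accept a steroid stopped the day before the last dose. Protocol 6.5.3 confines down-titration to Visits 8 to 13, and 4.3.4 bars it in Maintenance unless there is a safety concern. For a subject who completes 26 weeks, this would take a deviation or that exception.
- **Reduction after IVIg.** A reader might say that a subject who stops and then gets IVIg is also counted as reduced. That depends on how the phrase about all post-baseline doses is read. Protocol 4.3.2 normally keeps the baseline dose unchanged through Titration, so on a literal reading not every post-baseline dose was lower.
- **Other measures and traceability.** Discontinuation is not the only measure of the goal: reduction sits beside it, and 11.3.9 counts rescued subjects with a 95% CI. Listings 16.2.4.7, 16.2.4.8 and 16.2.6.1 let a reader trace individual cases.
- **Rescue as failure.** The protocol writes absence of rescue into the primary and durable-response endpoints but not into this one. Counting stops regardless of rescue is a coherent descriptive choice. The documents do not support calling it an error, or turning rescue into failure without changing the endpoint.

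The defence does not answer the missing stay-off condition. The companion rule has a comparable safeguard, and the listings do not correct the proportion in the table. Nor does any text say that discontinuation must be a subset of reduction; the case for that rests on the ordinary meaning of the two words.

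**Conclusion.** The point holds in limited form. SAP 11.3.10 counts a discontinuation although the steroid was restarted and stopped again before the last dose date, and although IVIg or a transfusion followed the stop. In the repeat-steroid case at or above the baseline dose, the same subject fails reduction, so the two lines of one table can contradict each other.

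The consequences are modest. This is an 'other' efficacy endpoint. SAP 8.3.5 plans no test, 11.3.10 asks for no confidence interval, and the 8.02-week primary hurdle does not use it. Each affected subject moves the proportion by 25 to 5 points, on the assumption of 4 to 19 baseline users. The result for a steroid still ongoing at the last dose date rests on reading 'all' to include steroids started on study, which the SAP should state. A reader should not conclude that every relapse is scored as success, or that such cases are hidden.

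**What to change.** In SAP 11.3.10:

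1. Define discontinuation as all baseline ITP medications stopped, with no ITP medication (as defined in that section) restarted or newly started through the last dose date of the 26-week period. This also settles which steroids the word 'all' covers.
2. State that discontinuation implies reduction, and align the reduction wording so that a subject who stops and stays off always meets it.
3. Report the discontinuation and reduction counts split by whether any rescue therapy, as defined in 11.3.9, was used after the stop or reduction. Show the count without later rescue next to the unconditional count. The protocol endpoint then keeps its meaning and rescue is visible in the same table.

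The cost is some SAP wording and one extra derivation. Medication doses and dates are already recorded under Protocol 6.5.6, and rescue use is recorded at the scheduled treatment visits under Protocol 7.2. The reported rate may be slightly lower. No study procedure changes.
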